### **Analysis of covariables**

The parameter values will be standardized for a body weight of 70 kg using an allometric model.

$$P(i) = P(std) \times \left( \frac{Weight(i)}{Weight(std)} \right)^{EXP}$$

Where  $P_i$  is the individual's parameter, weight ( $i$ ) is the individual's weight and  $P_{std}$  is the parameter in an individual with a standard weight of 70 kg. This standardization allows a better comparison of parameters in populations of different sizes. The exponent of EXP will be assumed to be 0.75 for the clarifications and 1 for the distribution volumes.

### **Pharmacodynamic analysis**

The use of rescue morphine in the PACU will be used as a measure to relate the methadone dose (mg / kg) with the analgesic efficacy using an EMAX model.

$$Morphine\ Rescue\ Dose\ (mg/kg) = SO \times \frac{Dose\ (mg/kg) \times Emax}{Dose\ (mg/kg) \times ED50}$$

$SO$  is the required morphine rescue without the use of methadone, EMAX is the maximum required morphine rescue dose and ED50 is the methadone dose that reaches half of this maximum morphine rescue dose. The data was modeled using NONMEM VII. A proportional term was used for variability between subjects. Additive and proportional terms were used to characterize the unknown residual variability. The convergence criterion was three significant digits.

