## Influence of aging on the perioperative dosage of methadone

### Introduction

Increasingly, elderly patients undergo anesthesia and surgery. There are multiple factors that affect the dosage of anesthetic drugs in this age group, such as the normal aging process, age-related morbidity and polypharmacy, commonly observed in the elderly patient (1). The older adult presents pharmacodynamic and pharmacokinetic changes associated with alterations in absorption, distribution, metabolism, and excretion, which commonly translate into an increase in the potency of the drugs, so significant dose reductions may be required(1-5).

Opioids are non-steroidal analgesic drugs widely used in the management of intra and postoperative pain. Numerous studies have described important changes in the pharmacokinetics and pharmacodynamics of these drugs in the elderly population (3,6,7). Morphine clearance, for example, is reduced by 50% in the elderly compared to the young adult, which may prolong the action of this drug in the first group (6). The potency of fentanyl or remifentanil increases progressively with age, requiring substantially lower concentrations in the elderly compared to a young adult to obtain the same effect (3,8).

Methadone is considered a first-line opioid in the treatment of chronic pain due to numerous advantages compared to other opioids (9). Methadone does not generate active metabolites after its liver biotransformation (10), it has a long half-life that translates into a prolonged effect and simple dosing schedules (10), it has antihyperalgesic and antiallodynic properties that give it great effectiveness in the relief of neuropathic pain (11). Despite these advantages, the use of methadone in the surgical population is comparatively less than other opioids such as morphine or fentanyl. Although the general recommendation for the use of opioids in the elderly is to decrease the doses, the great inter-individual variability characteristic of elderly patients and the greater susceptibility to adverse effects in this population, make anesthetic dosing challenging and requires a new approach, to establish more precise dosages in terms of effectiveness and safety. However, to date there are no pharmacokinetic or pharmacodynamic studies that allow standardizing a dose adjustment of methadone in the elderly patient.

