### Specific objectives:

- 1) Characterize the changes in methadone volumes and clearance, attributable to age in the adult population.
- 2) Characterize the changes in methadone potency, attributable to age in the adult population.
- 3) Design intraoperative methadone dosing schedules, according to the age of the patient.

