### **Pharmacokinetic analysis**

One, two and three compartment linear models will be used to fit the methadone plasma concentration data over time. Models will be parameterized in terms of elimination clearance, inter-compartment distribution clearance, central volume, and peripheral distribution volumes, as appropriate. Estimates of population parameters (clearance and volumes) will be obtained using nonlinear mixed effects models (NONMEM VII, Icon Development Solutions, [name], USA).

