### **Pharmacodynamic analysis**

The use of rescue morphine in the PACU will be used as a measure to relate the methadone dose (mg / kg) with the analgesic efficacy using an EMAX model. The data will be modeled using NONMEM VII. A proportional term will be used for variability between subjects. Additive and proportional terms will be used to characterize the unknown residual variability. The convergence criterion will be three significant digits.

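### The PD model's ED50 is an administered methadone dose, so an age effect on it would measure dose requirement, not the change in potency that objective 2 asks for

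*Combined protocol and SAP*

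**What the plan says.** Specific objectives: objective 1 concerns age changes in methadone volumes and clearance. Objective 2 is separate: "Characterize the changes in methadone potency, attributable to age in the adult population". Objective 3 builds on both: "Design intraoperative methadone dosing schedules, according to the age of the patient".

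Pharmacokinetic analysis: "Models will be parameterized in terms of elimination clearance, inter-compartment distribution clearance, central volume, and peripheral distribution volumes, as appropriate". Age is not mentioned.

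Analysis of covariables: the only covariate is body weight. "The exponent of EXP will be assumed to be 0.75 for the clarifications and 1 for the distribution volumes". Nothing is given for S0, Emax or ED50.

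Pharmacodynamic analysis (both occurrences): PACU rescue morphine is used "to relate the methadone dose (mg / kg) with the analgesic efficacy using an EMAX model". In the second occurrence S0 "is the required morphine rescue without the use of methadone", and "ED50 is the methadone dose that reaches half of this maximum morphine rescue dose". No covariate is placed on any of the three parameters.

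Sample size: age enters as a 20% fall in elimination clearance and as three bands of 20 patients. No figure is given for potency.

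**The concern.** The objectives treat kinetics and potency as two questions, but the PD model has an input that cannot separate them. If older patients reach higher methadone exposure from the same mg/kg dose, a smaller dose gives the same effect and the dose-based ED50 falls, even if the response to a given exposure is the same at every age. Reported under objective 2, that would be called a potency change.

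The label matters for objective 3. An analyst who reads the ED50 effect as pure potency could reasonably add the clearance or volume effect from objective 1 when deriving schedules, and so count the same kinetics twice. The plan does not say how the two results are to be combined.

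**Working it through.** **1. The plan's own figure.** There is none for an age effect on ED50. The nearest is the statement that about 50 patients detect a 20% lower clearance with 80% power. It cannot be reproduced, because no between-subject CV or alpha is given. As a guide, take 25 v 25 on log clearance with two-sided alpha 0.05 (assumed). Then SD = |ln 0.8| × √(25/2) / (1.96 + 0.84) = 0.223 × 3.54 / 2.80 = 0.28, a CV of about 29%. The figure concerns clearance only, so it gives no basis for objective 2.

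**2. How much PK can sit inside a dose-based ED50.** Assumptions (not in the documents): one compartment, IV bolus, half-life 6-36 h, effect driven by AUC from 0 to t, and the same response to a given exposure at all ages. The 20% clearance fall is from the Sample size section. A 20% volume fall is assumed for comparison.

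AUC(0-t) = (Dose/CL) × (1 − e^(−kt)), with k = CL/V. With equal potency, the ED50 ratio (old/young) equals the dose ratio that gives equal AUC:

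- clearance × 0.8: R = 0.8 × (1 − e^(−kt)) / (1 − e^(−0.8kt))
- volume × 0.8: R = (1 − e^(−kt)) / (1 − e^(−1.25kt))

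Half-life 6 h, t = 4 h: kt = 0.693 × 4/6 = 0.462 and 1 − e^(−kt) = 0.370.

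- clearance: 0.8 × 0.370 / 0.309 = 0.96
- volume: 0.370 / 0.439 = 0.84

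Half-life 36 h, t = 4 h: kt = 0.077. The same formulas give 0.99 and 0.81.

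| Exposure driving effect | Clearance × 0.8 | Volume × 0.8 |
|---|---|---|
| AUC 0-4 h | 0.96-0.99 | 0.81-0.84 |
| AUC 0-24 h | 0.84-0.96 | 0.84-0.97 |
| Total AUC | 0.80 | 1.00 |

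If clearance and volume both fell by 20%, k would not change and R would be 0.80 for any window. Over a short window volume dominates; over a long one clearance does. Objective 1 expects age may change both.

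**3. Double counting.** If the dose-based ratio is 0.80 purely from clearance and the clearance effect is then applied again, the schedule factor becomes 0.80 × 0.80 = 0.64. The plan does not propose this step, but nothing in it rules the step out.

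**4. Age on baseline rescue (S0).** The Introduction says "Morphine clearance, for example, is reduced by 50% in the elderly compared to the young adult", and the outcome is itself morphine, so S0 may differ by age. The documents give neither direction nor size.

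Assumed model: S0 × (1 − Emax × D/(D + ED50)) at the four planned doses, S0 0.15 mg/kg in younger patients, true ED50 0.1 mg/kg at all ages, Emax 1, residual SD 0.04-0.06 mg/kg, 10 younger and 5 older patients per dose. The root mean square error of the log ED50 ratio is √(bias² + SE²). With an S0 age term the bias is zero, so the error is the SE.

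- S0 10% lower in patients over 65. Without the term: bias ln 0.80 = −0.22, SE 0.38-0.57, error 0.44-0.61. With it: 0.51-0.77.
- S0 20% lower. Without the term: bias ln 0.63 = −0.47, SE 0.39-0.59, error 0.61-0.75. With it: 0.56-0.84.

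The term removes a possible bias at a cost in precision, and which choice is more accurate depends on facts the documents do not give.

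**The case against.** The best defence is that a dose-based ED50 is what a dosing study needs. The general objective is a set of dosing schedules by age, and the Introduction at one point speaks of pharmacokinetic and pharmacodynamic changes together raising drug potency. In that sense an ED50 in mg/kg is a legitimate result. The outcome is also PACU rescue, where the clearance share may be only 1-4%.

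Much of this stands. The dose scale is defensible if the result is called dose requirement. It does not settle objective 2, which is listed apart from volumes and clearance, and the Introduction also describes potency by the concentration needed for a given effect. Nor is the PK share always small, since a volume change acts early.

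A reader might infer three stronger things that the documents do not support.

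- **That the plan cannot answer objective 2.** Age is the research question, the age bands are filled by design, and mixed-effects models with a covariate section are planned. An age term can be added; its place and form are simply unwritten. For clearance, the Sample size section already implies one.
- **That a baseline rescue difference will be mistaken for potency, so that age on S0 must be mandatory.** This would follow if age were placed on ED50 alone, which the plan does not propose. Step 4 of the working shows the term is a trade-off.
- **That the PD equation is wrong because Dose appears as a product in numerator and denominator and cancels.** A plus sign may have been lost when the PDF was read. It should be confirmed, and it carries no weight here.

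**Conclusion.** The point holds in this form: the PD input and the definition of ED50 are on the dose scale, while objective 2 asks for potency apart from kinetics. An age effect on this ED50 would include any age effect on methadone exposure. That follows from the text alone.

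The size rests on the one-compartment assumptions above. With no potency change at all, the apparent ED50 ratio could lie anywhere from about 0.99 to 0.80, depending on whether clearance or volume changes and over what window effect is driven. A real kinetic change in the other direction would move it above 1.

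This is a matter of interpretation and specification that should be settled before analysis. It does not invalidate the design or the data.

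**What to change.** In both Pharmacodynamic analysis sections and in Analysis of covariables:

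1. Choose the scale for objective 2. Either (a) use each patient's PK-model-predicted methadone exposure over the PACU period as the PD input, set to zero for placebo, and estimate the age effect on EC50; or (b) keep mg/kg, report the ED50 result as an age effect on dose requirement, and state that the PK age effect is not applied again when schedules are derived.
2. Write the age terms for the PK and PD models, naming the parameters and the functional form.
3. Report the age ratio with the bootstrap interval already planned under Model fit quality.
4. Fit age on S0 (informed by the placebo group) and age on Emax as sensitivity analyses.
5. Check the printed equation against the source file.

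Cost: SAP wording and a little more modelling. No patients or samples are added, because five samples per patient are already planned. Option (a) carries PK-model error into the PD result. The interval will be wide: with equal and balanced allocation, which the plan does not state, only 20/4 = 5 patients over 65 receive placebo. In the dose-scale model of the working (Emax 1), taking S0 as equal across ages, the 95% interval is the estimate multiplied and divided by 2.0-2.9, or by 2.5-4.0 once age is also on S0. The result is better presented as an estimate than as a test.

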### **Sample size**

Sample size calculations were estimated using a simulation-based approach and previous work with similar methodology. We estimate that approximately 50 patients (5-6 samples per patient) are required to detect the effect of age, assuming a 20% proportional decrease in elimination clearance, with 80% potency. To achieve an adequate representation of all age groups, a number of 60 patients will be required, distributed among 20 patients between 18 and 40 years, 20 patients between 41 and 65 years and 20 patients > 65 years. The PharmPow package used for these calculations is available at <http://cran.r-project.org/web/packages/PharmPow/PharmPow.pdf>.

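### The rescue-morphine model defines Emax and ED50 on the rescue dose instead of on its reduction, so Emax repeats S0 and the stated ED50 is generally not the model's ED50

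*Combined protocol and SAP*

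**What the plan says.** The combined protocol and SAP has two sections headed Pharmacodynamic analysis. Both say that PACU rescue morphine will be used "to relate the methadone dose (mg / kg) with the analgesic efficacy using an EMAX model". The first gives no equation and no parameter definitions.

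The second, after Analysis of covariables, gives both. S0 (printed SO) "is the required morphine rescue without the use of methadone". The other two parameters are defined together: "EMAX is the maximum required morphine rescue dose and ED50 is the methadone dose that reaches half of this maximum morphine rescue dose". The equation, as it appears in the text available, is Rescue = S0 × (Dose × Emax)/(Dose × ED50).

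No other section corrects these definitions. Two of the Specific objectives depend on this part of the plan: "Characterize the changes in methadone potency, attributable to age in the adult population" (Objective 2) and "Design intraoperative methadone dosing schedules, according to the age of the patient" (Objective 3).

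**The concern.** Methadone is expected to lower the need for rescue morphine, so the model has to describe a fall from S0. That takes three quantities: the starting level, the largest possible fall, and the dose giving half of that fall. The text supplies the first but defines the other two on the rescue dose itself. The largest rescue dose occurs without methadone, which is already S0. The size of the fall is left with no parameter, and ED50 becomes the dose that halves rescue.

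This is the only pharmacodynamic model in the plan. ED50 is its natural measure of potency for Objective 2; that link is my inference, since the objectives name no potency measure. Objective 3 builds dosing schedules by age on the results. If an ED50 is estimated under one meaning and reported or used under the other, the stated potency is wrong by a factor that depends on the maximum effect.

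A secondary point is that the equation as it appears does not depend on dose at all.

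**Working it through.** **Inputs.** The definitions and equation come from the second Pharmacodynamic analysis section. The doses 0, 0.05, 0.1 and 0.2 mg/kg come from Distribution by random groups. The documents give no values for S0, Emax, ED50 or the maximum fractional reduction f, so all such values below are assumptions. The plan states no figure on this point to reproduce.

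**1. What the definitions imply.** If rescue falls with methadone dose, its maximum is at dose 0. Emax as defined in the text is therefore S0, and ED50 as defined is the dose D at which rescue equals S0/2.

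**2. Comparison with the Emax-model ED50.** Take the inhibitory model R(D) = S0 − Emax × D/(ED50 + D), with Emax the maximum reduction and f = Emax/S0. Setting R(D) = S0/2:

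f × D/(ED50 + D) = 0.5, so D = ED50 × 0.5/(f − 0.5).

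This has a solution only for f > 0.5. At D = ED50, the rescue remaining is (1 − f/2) × S0.

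| Assumed f | Text ED50 ÷ model ED50 | Rescue left at model ED50, as share of S0 |
|---|---|---|
| 1.0 | 1.00 | 50% |
| 0.9 | 1.25 | 55% |
| 0.8 | 1.67 | 60% |
| 0.7 | 2.50 | 65% |
| 0.6 | 5.00 | 70% |
| ≤ 0.5 | no such dose | 75% or more |

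Only f = 1 (complete suppression of rescue) gives the half that the text describes, and there Emax = S0 is redundant.

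**3. Worked example.** Assume S0 = 0.15, Emax = 0.12 and ED50 = 0.08 mg/kg, so f = 0.12/0.15 = 0.8. The dose that halves rescue is 0.08 × 0.5/0.3 = 0.133 mg/kg. Check: 0.12 × 0.133/(0.08 + 0.133) = 0.075 = S0/2. The two meanings give 0.08 and 0.133 mg/kg for the same curve.

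**4. The equation (secondary).** Predicted rescue (mg/kg) with the same assumed values:

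| Form | 0 | 0.05 | 0.1 | 0.2 | Individually identifiable |
|---|---|---|---|---|---|
| As it appears | 0/0 | 0.225 | 0.225 | 0.225 | 0 of 3 |
| Plus sign in the denominator only | 0 | 0.007 | 0.010 | 0.013 | 1 of 3 (ED50) |
| S0 − Emax × D/(ED50 + D) | 0.150 | 0.104 | 0.083 | 0.064 | 3 of 3 |

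- As it appears, Dose cancels and every active group gets S0 × Emax/ED50 = 0.15 × 0.12/0.08 = 0.225. Only that combination can be estimated.
- With a plus sign in the denominator only, placebo rescue is 0, against the definition of S0. Rescue rises with dose, and S0 and Emax enter only as a product.
- With plus signs in both places and positive Emax, rescue starts at S0 and rises with dose.
- The subtractive form falls as intended, but its Emax is the maximum reduction, not a rescue dose.

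Identifiability is the rank of the parameter Jacobian without noise (1, 2 and 3 for the three rows). It checks the form only and says nothing about precision with the planned number of patients.

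**The case against.** The strongest reply is that this is loose wording around a conventional model. Every operator in the equation appears as a multiplication sign. If the original has a minus before the fraction and a plus in the denominator, it is the standard inhibitory Emax model, and an analyst would code it correctly whatever the prose says. This may be so, and it cannot be settled from the text available. The equation is therefore a matter for checking against the original. The definitions, however, are in running prose. Under a correct equation they would still contradict it, except at f = 1, which the plan does not state.

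Second, the multiplier 0.5/(f − 0.5) depends only on f. If f is above 0.5 and the same at all ages, it cancels, and the old-to-young ratio of ED50 is the same under either meaning. That stands: the relative age comparison is affected only if f varies with age. For example, equal model ED50s with assumed f of 0.9 and 0.7 would give text ED50s differing by 2.5/1.25 = 2-fold, so a difference in maximum effect would be read as one in potency. The absolute ED50, which a dosing schedule would use, differs between the meanings even when f is constant, unless f = 1.

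Third, the dose that halves rescue is a coherent quantity when f > 0.5. That also stands. It may be reported, but under its own name and not as the ED50 of the Emax model.

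Finally, the size rests wholly on assumed f. This is true; at f = 1 the discrepancy is zero.

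**Conclusion.** The concern holds. As written, Emax duplicates S0, no parameter describes the maximum reduction in rescue, and the stated ED50 matches the Emax-model ED50 only under complete suppression. Over the assumed range of f from 0.9 down to 0.6, the two differ by a factor of 1.25 to 5; at f of 0.5 or less, the stated ED50 does not exist. This rests on the model's premise that methadone does not increase rescue.

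The practical consequence is conditional. Results change only if the text's definition is used for reporting or dosing. The loss of dose from the equation is secondary until the operators have been checked. The sample size is unaffected, because it is the number "required to detect the effect of age, assuming a 20% proportional decrease in elimination clearance", a pharmacokinetic target.

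This should be corrected before the model is fitted: it is a wrong definition in the only model that serves the potency objective, and correcting it is nearly free.

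**What to change.** Check the operators against the original document. Then state one inhibitory Emax model, for example:

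- absolute form: Rescue = S0 − Emax × D/(ED50 + D), with Emax in mg/kg; or
- fractional form: Rescue = S0 × [1 − Emax × D/(ED50 + D)], with 0 ≤ Emax ≤ 1.

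The two give identical predictions when the fractional Emax equals the absolute Emax divided by S0 (0.12/0.15 = 0.8 in the example above).

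Keep S0 as it is. Define Emax as the maximum reduction in rescue morphine, absolute or fractional to match the form chosen. Define ED50 as the methadone dose giving half of that maximum reduction. If ED50 is the intended potency measure for Objective 2, say so. If the dose that halves rescue is also wanted, give it a separate name and derive it from the fitted parameters.

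The cost is a correction to one equation and two definitions, with no extra patients, no new data and no change to the sample size.

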### **Model fit quality**

The Bootstrap methods, incorporated within the NONMEM program, will provide a means of evaluating the uncertainty of the parameters (13). A total of 1000 repetitions will be used to estimate the confidence intervals of the parameters. A Visual Predictive Verification (VPC) (14), a modeling tool that estimates concentration prediction intervals and graphically superimposes these intervals on concentrations observed after a standardized dose, will be used to assess how well the model predicts the distribution of observed methadone concentrations. The VPC simulation will be performed using 1000 subjects with characteristics similar to the patients studied.

### **Sample size**

Sample size calculations were estimated using a simulation-based approach and previous work with similar methodology. We estimate that approximately 50 patients (5-6 samples per patient) are required to detect the effect of age, assuming a 20% proportional decrease in elimination clearance, with 80% potency. To achieve an adequate representation of all age groups, a number of 60 patients will be required, distributed among 20 patients between 18 and 40 years, 20 patients between 41 and 65 years and 20 patients > 65 years. The PharmPow package used for these calculations is available at <http://cran.r-project.org/web/packages/PharmPow/PharmPow.pdf>.

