### **Distribution by random groups**

Patients who agree to participate will be randomized into four groups according to the dose of intravenous methadone to be received during anesthetic induction. Group P (placebo), Group M1 (0.05 mg / kg), Group M2 (0.1 mg / kg), and Group M3 (0.2 mg / kg). The random sequence will be generated on a research laboratory computer and will be stored in an encrypted file. This information will be known exclusively by a member of the research team present during the surgery, who will hand over preparing the corresponding medicine in a 20 cc syringe and hand it over to the treating anesthesiologist.

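### The 80% power for clearance needs about 50 patients with methadone concentrations, but the 60 planned include a placebo group; with four equal groups only about 45 inform clearance.

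*Combined protocol and SAP*

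**What the plan says.** The power statement is in the Sample size section of the combined protocol and SAP: "We estimate that approximately 50 patients (5-6 samples per patient) are required to detect the effect of age". The size of that effect and the power are given as "assuming a 20% proportional decrease in elimination clearance, with 80% potency" (potency is evidently a translation of power). The total is then raised for a different reason: "To achieve an adequate representation of all age groups, a number of 60 patients will be required", split as "20 patients between 18 and 40 years, 20 patients between 41 and 65 years and 20 patients > 65 years". The section does not mention the placebo group or dropout. It also does not say whether 50 and 60 count everyone enrolled or only those given methadone.

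Under Distribution by random groups, "Patients who agree to participate will be randomized into four groups according to the dose of intravenous methadone". One of the four groups receives placebo and three receive methadone. No allocation ratio is stated, nor whether the groups are balanced within age bands.

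The Pharmacokinetic analysis section names the data behind clearance: "One, two and three compartment linear models will be used to fit the methadone plasma concentration data over time".

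**The concern.** A patient who receives no methadone has no methadone concentration curve and so carries no information on methadone clearance or its relation to age. The Materials & Methods section also excludes recent opioid users, so placebo patients should not have methadone from another source. The number that matters for this power claim is therefore the number treated with methadone, not the number enrolled.

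This is the only power statement in the plan, and it supports specific objective 1, the effect of age on volumes and clearance. Someone comparing 60 planned with 50 needed would infer a 20% margin. If the four groups are equal, there is a 10% shortfall instead, and the stated 80% is not supported for the design as written.

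**Working it through.** **Inputs**
- Required number: about 50 patients, for a 20% lower clearance at 80% power (Sample size).
- Total planned: 60, as 20 in each of three age bands (Sample size).
- Groups: four, one of them placebo (Distribution by random groups).
- Allocation ratio: not stated; 1:1:1:1 assumed.
- Significance level: not stated; two-sided 5% assumed, with one-sided 5% and two-sided 1% as the range.
- Dropout: not stated; none assumed.

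**1. Can the plan's 50 be reproduced?** Not properly. The simulation's variability, residual error, age contrast and significance level are not given. As a rough plausibility check, compare two equal age groups on log clearance, with δ = |ln 0.8| = 0.223, σ² = ln(1 + CV²) and

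n per group = 2 × (1.960 + 0.842)² × σ² / δ², rounded up.

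The total is 40, 52, 56 and 74 for an assumed between-subject CV of 25, 29, 30 and 35%. A requirement of about 50 is thus attainable at a CV near 29%, but this does not reproduce the simulation. Below, 80% at N = 50 is taken as given.

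**2. Patients who inform clearance**
- Equal groups: 60 × 3/4 = 45 on methadone and 15 on placebo.
- Per age band, if placebo is balanced across bands: 45/3 = 15.
- Shortfall: (50 − 45)/50 = 10%.
- Most placebo patients that still leave 50: 60 − 50 = 10, or 1 in 6 of those enrolled.
- Enrolment that gives 50 on methadone at equal allocation: 50/0.75 = 66.7, so 67 (or 68 as 4 × 17, with 51 on methadone).

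**3. Rescaled power.** Assume information on clearance is proportional to the number of methadone patients:

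power(n) = Φ[(z_α + z_0.80) × √(n/50) − z_α]

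| Level | Calculation at n = 45 | Power |
|---|---|---|
| two-sided 5% | Φ(2.802 × √0.9 − 1.960) = Φ(0.698) | 75.7% |
| one-sided 5% | Φ(2.486 × √0.9 − 1.645) = Φ(0.714) | 76.2% |
| two-sided 1% | Φ(3.417 × √0.9 − 2.576) = Φ(0.666) | 74.7% |

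For contrast, if all 60 were informative, two-sided 5% power would be Φ(2.802 × √1.2 − 1.960) = 86.6%.

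**4. Detectable fall at n = 45 with 80% power**
- Log scale: 1 − 0.8^√(50/45) = 21.0%.
- Linear scale: 20% × √(50/45) = 21.1%.

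**5. Sensitivity to the word approximately** (two-sided 5%)
- If the true requirement is 45, power at 45 is 80%.
- If it is 55, power at 45 is Φ(2.802 × √(45/55) − 1.960) = 71.7%.
- For 45 patients to give 80%, 50 would have had to give Φ(2.802/√0.9 − 1.960) = 84.0%.

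**The case against.** The plan never says that its 50 are methadone recipients. The Blood Sampling section has five samples drawn from each patient and makes no exception for placebo, so the per-patient sampling phrase does not settle who is counted. The simulation may already have included a placebo group. The allocation ratio is also unstated, and with 10 or fewer placebo patients there is no deficit. On this view the text has a gap and not two conflicting figures, and 45 may lie within what the plan means by approximately 50.

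The rescaling is open to challenge too. It needs a significance level the plan does not give, and it assumes the same information per patient in the simulated 50 as in the planned 60. Information on an age effect also depends on the spread of ages, which the 20/20/20 split may change in either direction. Finally, the aim is to build a model with bootstrap uncertainty, and placebo patients have a real use in the rescue-morphine model, where they inform morphine need without methadone.

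Much of this stands as limits on size. The shortfall depends on allocation, the loss is small, and the power figures are approximate. It does not remove the point. Only methadone recipients can support a power claim about clearance, equal groups are the natural reading when no ratio is given, and nothing suggests a smaller placebo group. The stated reason for going from 50 to 60 is age representation, not placebo. The number 45 meets the claim only at the favourable end of the 45 to 55 range. If the simulation did allow for placebo, the section still needs to say so.

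**Conclusion.** The concern holds. Under equal allocation about 45 patients inform clearance, against the plan's own requirement of about 50, so the 80% is not supported for the design as written. The likely cost is about 4 percentage points of power (to about 76%, or 72% to 80% if the requirement is anywhere from 55 to 45), or a detectable fall of about 21% where the plan states 20%.

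The count of 45 rests on equal allocation; the shortfall itself needs only more than 10 placebo patients among the 60, and a requirement of 50 that refers to methadone-treated patients. The power figures rest in addition on an assumed 5% level and on information proportional to the number treated. The point concerns the clearance claim only and says nothing against having a placebo group. It should be fixed, but it does not threaten the study.

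**What to change.** In the Sample size section:
- State the allocation ratio and whether placebo is balanced across the three age bands.
- Express the requirement in methadone-treated patients, with the total enrolled given separately.
- Re-run the PharmPow simulation with the number who will contribute concentrations (about 45 at 1:1:1:1) under the planned design of three dose levels, five samples per patient and two sampling schedules. Report whatever power or detectable fall in clearance it gives.
- If the existing simulation already allowed for placebo, say so and give the number of methadone patients it used.

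The cost is one re-run of an existing simulation and a reworded paragraph, with no extra patients and no change in conduct. The likely price is a slightly less favourable stated power or detectable effect.
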